### 13.2. Treatment Period (Week 1 to Week 48)

### 13.2.1. Day 1 (Visit 4)

Following completion of the 4-week screening period, subjects will enter the treatment period and will receive pegcetacoplan. The following assessments outlined in the schedule of events (Section 4) will be performed:

Prior to treatment:

- Procure 3 previously collected consecutive uPCR samples
- Eligibility confirmation
- Triplicate 12-lead ECG at -45, -30, and -15 minutes predose
- Concomitant medications collection
- Vital sign measurements

- Urinalysis (See schedule of events for details)
- Blood tests (see schedule of events for details)
- Pregnancy (β-HCG)
- Urine pregnancy test, if applicable
- Predose PK collection (within 1 hour before dose)
- Dispense investigational product and infusion materials
- Train subject to perform home infusion
- Full physical examination

### Following Treatment:

- Subjects will be contacted via phone by study staff 6 hours after the study treatment to collect safety information
- Vital sign measurements at 30 minutes, 2 hours, and 4 hours post dose
- Injection Site Assessment
- Collect AEs
- Dispense 3 uPCR containers for consecutive collection

### 13.2.2. Week 2 to Week 48 (Visits 5-15)

Subjects will self-administer once daily SC doses 360 mg of pegcetacoplan and will attend the investigator site at Visits 5-15 where the assessments outlined in the schedule of events (Section 4), will be performed.

Visit window:  $\pm 2$  days.

Research nurses or other appropriately qualified research personnel will administer the SC infusions until the subject has been qualified to conduct self-administration. Following self-administration qualification, subjects may self-administer the SC infusions. The subject will continue to self-administer infusions at the clinic on those days when a clinic visit occurs and at an off-site location convenient to the subject on all other days. Subjects have the opportunity to transition to a biweekly 1080 mg SC infusion of pegcetacoplan, as early as Week 24 of Part A of the study. If this occurs, the subject will need to have 3 transition visits (T1, T2, and T3), the details of which are provided in Table A1 of Appendix 1.

The following assessments will be performed prior to investigational product administration:

- Procure 3 previously collected consecutive uPCR samples (except Visit 15)
  - Arrange courier pickup for all biweekly triplicate uPCR samples during non-clinic visit weeks
- Dispense 24-hour urine container at Visit 14 (for urine collection within 2 weeks prior to Visit 15)
- Vital sign measurements (to be performed prior to ECG and venipuncture)

- Triplicate 12-lead ECG 15 minutes predose
  - Visit 15: Triplicate 12-lead ECG at -45, -30, and -15 minutes predose
- PK sample predose (within 1 hour before dosing) to coincide with the 15 min predose ECG
- Concomitant medications review
- AE collection and review
- Urinalysis collection (See schedule of events for details)
- eGFR assessment
- Pregnancy (β-HCG) (Visit 15 only), if applicable
- Blood tests (see schedule of events for details)
- Urine pregnancy test, if applicable
- Physical examination (Full exam at Visit 15 only)
- Vaccination Titer Serum Sample (Visit 7 only)
- Vaccination(s) Booster (Visit 7 only)
- Dispense investigational product and infusion materials
- Observe Infusion of investigational product

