## 9.2. Study Endpoints

## 9.2.1. Primary Efficacy Endpoints

• Proteinuria reduction from baseline to Week 48, based on urinary protein-to-creatinine ratio (uPCR)

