### **10.1.** Transition to Twice-Weekly Dosing

Patients are able, at the discretion of the sponsor, to transition to twice-weekly dosing with 1080 mg pegcetacoplan prior to the Long-Term Extension Phase, but not earlier than Week 24. If a dose transition occurs during Part A, the subject will need to follow the dose transition visits, outlined in Table 2 below. Dose can be adjusted, as needed, to maintain clinical response.

Transition Visits (T1, T2, and T3) should be scheduled for 1, 2, and 4 weeks after the first day on which their dose was adjusted. Additionally, subjects should be instructed to skip their Core Study Phase dose the day before the visit at which their dose will transition.

**Table 2:** Part A, Dose Transition Visits

		Dose Transition Visits	
Study Week	T+1W	T+2W	T+4W
Study Day	T+7D	T+14D	T+28D
Study Visit	T1	T2	Т3
Visit Window (±Days)	2	2	2
Physical examination a			
Triplicate 12-lead electrocardiogram			
Pegcetacoplan administration b	X	X	X
Injection site assessment c	X	X	X
Concomitant medications	X	X	X
Vital sign measurements d	X	X	X
Urinalysis	X	X	X
Return uPCR samples		X	X
Bloode	X	X	X
Pharmacokinetics f	X	X	X
Antidrug Ab assays g			X
Hematology and chemistry	X	X	X
PD for Complement profile f	X	X	X
Pregnancy (β-HCG and FSH)			
Urine pregnancy test h			X
Adverse events	X	X	X
Drug Dispensation for Home Administration	X	X III. in a sign of a	X

Abbreviations:  $\beta$ -HCG = beta human chorionic gonadotropin; ECG = electrocardiogram; IP = investigational product; PD = pharmacodynamic; PI = primary investigator; SC = subcutaneous; uPCR = urine protein-to-creatinine ratio; WOCBP = women of childbearing potential.

- a Symptom-driven physical examinations may be performed at unscheduled time points if deemed necessary by the PI.
- b Subjects will self-administer SC pegcetacoplan, after receiving appropriate training by a research nurse or other personnel. During site visits subject will self-administer pegcetacoplan at the site if the visit occurs on a dosing day. If the visit falls on a nondosing day, no IP administration is needed.
- c Between site visits, subjects will be instructed to report any injection site reaction to the study coordinator.

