### 13.1. Screening (Week –4 to Week –2)

The subject will be screened to confirm that the subject selection criteria for the study has been met. Informed consent will be obtained at screening prior to any study-related procedures being conducted (see Section 17.3.3). Patients with sufficient previous medical history (see Section 10 for details) will begin the 4-week screening period.

A screen failure is a subject who has given informed consent and failed to meet at least one of the inclusion and/or met at least 1 of the exclusion criteria and has not been randomized or administered investigational product(s).

Screening procedures are listed in the Schedule of Events in Section 4.

The following assessments will be performed at each visit:

- Informed consent.
- Demographics
- Medical history (including current angiotensin-converting enzyme inhibitor/angiotensin-receptor blocker therapy) (Visit 3a only)
- Review of inclusion/exclusion criteria
- Physical examination
- Begin 24-hour urine collection during scheduled clinic visit (Visit 3a only)
- Triplicate 12-lead ECG
- Prior and concomitant medications
- Vital sign measurements
- Urinalysis assessment (see schedule of events for details)
- Blood tests (see schedule of events for details)
- β-HCG pregnancy test, if applicable
- Follicle-stimulating hormone, HIV, HCV, HBsAg (see schedule of events for details)
- AE collection
- Vaccination Titer Serum Sample (Visit 3b only)

- Vaccination (see schedule of events for details)
- Dispense 3 uPCR containers for consecutive collection (Visit 3b only)

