#### After investigational product administration:

- Subjects will be contacted via phone by study staff 6 hours after the study treatment to collect safety information (Visit 15 only)
- Vital sign measurements at 30 minutes post dose
  - Visit 15 only: Vital sign measurements to be measured at 30 minutes, 2 hours, and 4 hours post dose
- Injection Site Assessment
- Collect AEs
- Dispense uPCR containers for consecutive collection
  - 3 uPCR containers (Visit 5 and 15 [for subjects entering the follow-up period]), 6
     uPCR containers (Visits 6-10, Visit 14, and, for subjects entering Part B, Visit 15), 9 containers (Visits 11-13)

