### 16.2.2.1. Primary Endpoint

Changes from baseline in proteinuria, percentage changes from baseline in proteinuria, and percentage change in mean proteinuria is the primary efficacy endpoint. They will be calculated by using mean of the 3 spot uPCR samples collected for baseline (Day 1) and the subsequent treatment visits. In addition, these calculations will be repeated using the 24-hour urine proteinuria sample which is collected at baseline (Day 1) and Week 48. If additional unscheduled 24-hour urine samples are collected then these will be included as well.

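### The Week 48 spot uPCR row will normally be empty, and the 24-hour uPCR row that covers Week 48 has a window that contradicts its own interval

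*Protocol*

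**What the plan says.** The primary endpoint in Protocol 9.2.1 is "Proteinuria reduction from baseline to Week 48, based on urinary protein-to-creatinine ratio (uPCR". On the calculation of changes in proteinuria, Protocol 16.2.2.1 states: "They will be calculated by using mean of the 3 spot uPCR samples collected for baseline (Day 1) and the subsequent treatment visits". It adds that "these calculations will be repeated using the 24-hour urine proteinuria sample which is collected at baseline (Day 1) and Week 48", and then: "If additional unscheduled 24-hour urine samples are collected then these will be included as well". SAP 6.1 tabulates both urine sources.

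The collection schedule treats Week 48 (Visit 15) differently from the other treatment visits:

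- Protocol 13.2.2 lists, before dosing at Visits 5-15: "Procure 3 previously collected consecutive uPCR samples (except Visit 15".
- The spot-sample return cell at Week 48 is blank in both Table 1 and Table A1.
- Visit 14 supplies two triplicate sets, while Visits 11-13 supply three. The protocol lists 6 "uPCR containers (Visits 6-10, Visit 14, and, for subjects entering Part B, Visit 15), 9 containers (Visits 11-13".
- A 24-hour collection is scheduled for Week 48. Section 14.1.7 allows it up to 2 weeks before Visit 15.

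SAP 13.4.2 nevertheless has a Week 48 spot row, Days 329 to <343. SAP 13.4.1 gives the 24-hour Week 48 row a target of Day 336, a window of Day 2 to <343 and an interval of 14. SAP 13.4 assigns every post-baseline record to a visit. If several fall in one window it keeps the record nearest the middle of the interval, with ties going to the earlier record.

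The date of the 24-hour baseline also varies. It is Day 1 in 16.2.2.1 and SAP 13.4.1. Section 13.1 says "Begin 24-hour urine collection during scheduled clinic visit (Visit 3a only", which Table 1 places at Day -28 with a window of 0. Section 14.1.7 says Visit 3a but also within 2 weeks of the first dose.

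**The concern.** The measure named first for the primary endpoint is not routinely collected at the endpoint's own time point, and the measure that is collected there has a mapping rule that cannot be applied as printed. SAP 2.0 reports Part A + B for subjects who rolled over, so its Week 48 rows are in use even though Part A was analysed under SAP 1.0.

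Three things are at stake in those tables. The spot cell at Week 48 would be empty, or would hold only a few atypical subjects. The 24-hour cell could hold a mid-study value labelled Week 48. And SAP 6.2 does not say whether the <200 mg/g, <500 mg/g and 30%/50% reduction tables use spot or 24-hour values, so a cell that is empty by design could be read as treatment failure.

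**Working it through.** **1. Spot sets supplied against sets needed.** Sets are biweekly and each uses 3 containers.

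| Dispensed at | Weeks to next visit | Sets needed | Containers | Sets supplied |
|---|---|---|---|---|
| Visits 6-10 | 4 | 2 | 6 | 2 |
| Visits 11-13 | 6 | 3 | 9 | 3 |
| Visit 14 (Week 42) | 6 | 3 (Weeks 44, 46, 48) | 6 | 2 (Weeks 44, 46) |

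The last routine set is Week 46, Day 322 ±3. If the ±3 days apply to the first of the three samples, the run starts on Days 319-325 and ends by Day 327. That lies inside the Week 46 window (315 to <329) and outside the Week 48 window (329 to <343). The next routine set, for subjects in follow-up, is Week 50 (Day 350 ±3, so from Day 347). Routine triplicates in Days 329-342: 0.

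Exceptions: unscheduled samples, and late Part A dose transitions. Table 2 has spot returns at T2 and T3, and the transition visits "should be scheduled for 1, 2, and 4 weeks after the first day on which their dose was adjusted". A return in Days 329-342 needs a transition on Days 315-328 (T2, minus 14) or 301-314 (T3, minus 28), so on Days 301-328.

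**2. The printed 24-hour interval.** Width = upper bound minus lower bound.

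| Row | Bounds | Width | Printed |
|---|---|---|---|
| Part A Week 48 | 2 to <343 | 341 | 14 |
| Part B Week 24 | 2 to <252 | 250 | 251 |
| Part B Week 48 | 252 to <420 | 168 | 168 |

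The other first post-baseline rows in SAP 13.4 agree to within 1 day. The Part A Week 48 row does not.

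**3. Compliant Week 48 24-hour days.** Visit 15 falls on Days 334-338 (336 ±2), and collection may be up to 14 days earlier: Days 320-338.

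**4. If the bounds are right.** Midpoint of Days 2-342 = (2 + 342)/2 = 172. The compliant day nearest the midpoint is Day 320, at 320 - 172 = 148 days. Day 24 is also 148 days away and wins the tie as the earlier record. Any sample on Days 24-319 (296 days) therefore displaces every compliant sample. Table 1 schedules no 24-hour collection there, so this needs an ad hoc one.

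**5. If 14 days is right.** The window is 343 - 14 = 329 to <343. Permitted days that it excludes:

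| Visit 15 on | Permitted days (15) | Excluded |
|---|---|---|
| Day 334 | 320-334 | 9 |
| Day 336 | 322-336 | 7 |
| Day 338 | 324-338 | 5 |

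**6. Part B Week 24.** Bounds and interval agree to within a day, but the midpoint is (2 + 251)/2 = 126.5 against a target of Day 168.

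**7. Responder cell if spot is the source.** With no scheduled sample, the routine Week 48 cell is 0/n if missing counts as non-response (SAP 6.2), or 0/0 if only subjects who could be assessed are counted (SAP 6). SAP 6.2 puts the non-response sentence in the responder paragraph and does not say whether it extends to the <200 mg/g remission table.

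**8. Part B spot baseline.** SAP 13.3 takes the last value on or before the first Part B dose, usually the Week 46 set. Its age at Day 336 is 336 - 327 = 9 to 336 - 319 = 17 days. If the ±3 days bound the whole run, it ends by Day 325 and the range is 11-17.

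**The case against.** The strongest reply is that the schedule is deliberate. The exception for Visit 15, the blank cells and the container count all agree, and a 24-hour collection takes the place of the spot set. Section 9.2.1 says only uPCR, and both 16.2.2.1 and SAP 6.1 prespecify the 24-hour value. This stands. A reader might infer that the primary endpoint is not measured at Week 48; the documents do not support that.

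Second, displacement by a mid-study sample is hypothetical. It needs an unscheduled collection, and it needs the midpoint taken from the printed bounds. If the tie rule refers to a 14-day interval ending before Day 343, the centre is close to Day 336. This also stands in part: the 296 days count calendar days, not likelihood. But the Interval column elsewhere is the width of the bounds, so one of the two entries is wrong, and 16.2.2.1 expressly brings unscheduled samples in.

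Third, one might say that the Part B Week 24 row has the same fault. It does not: it shares only the off-centre midpoint, and a Day 2 lower bound is the SAP's convention for a first post-baseline row.

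Fourth, the baseline dates conflict on paper, but SAP 13.3 takes the last value on or before first dose, and the only scheduled pre-dose 24-hour sample is at Visit 3a. That largely settles the analysis and leaves wording.

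Fifth, the urinalysis list in 14.1.9.4 includes a PCR, which might seem to fill the gap. The Table 1 urinalysis footnote lists ACR and not PCR, and in any case one value is not the mean of three.

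**Conclusion.** The point holds as a specification fault in descriptive tables. No routine spot triplicate falls in the Week 48 spot window, so that row will normally be empty in the Part A + B output. The 24-hour row that does cover Week 48 carries a width of 341 days against a printed 14. One reading lets an ad hoc sample from Days 24-319 stand as Week 48; the other excludes 7 of 15 permitted days for a Day 336 visit (9 for Day 334, 5 for Day 338). The unnamed urine source in SAP 6.2 leaves the Week 48 responder cell open to 0/n or 0/0 if spot values are used.

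No hypothesis test depends on this. The day counts assume nominal visit days with the stated windows and, for the Week 46 run, that ±3 days apply to its first sample. A reader might go further and infer that the reported Part A result is wrong. That cannot be said: SAP 1.0 governed that analysis and is not among the documents. Nor do they show that any unscheduled 24-hour sample was taken.

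**What to change.** 1. **SAP 13.4.1 and 13.4.** Set the 24-hour Week 48 window to Days 320 to <343 (interval 343 - 320 = 23), which holds every compliant day. Select the record nearest the target day (Day 336; Day 168 for Part B Week 24) in place of the interval midpoint. Amend the SAP 13.4 sentence that assigns all post-baseline records, so that 24-hour samples outside the window are summarised or listed as unscheduled and not as Week 48. Record this departure from Protocol 16.2.2.1 in SAP 15.1, which now reads as not applicable.
2. **SAP 6.2.** Name the urine source for the <200 mg/g, <500 mg/g and 30%/50% analyses, with the 24-hour value at Week 48. State that a Week 48 spot cell with no scheduled sample is outside the denominator and is not non-response.
3. **SAP 13.4.2.** Footnote the Week 48 spot row as not routinely scheduled. Note that the existing Week 46 row is the last routine Part A spot value and the usual Part B spot baseline, about 9-17 days old at Day 336 under the stated assumption.
4. **24-hour baseline date.** Reconcile Protocol 14.1.7 and 16.2.2.1 and SAP 13.4.1 with Table 1, keeping the SAP 13.3 rule. This is wording only.

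No change to sample collection is proposed. Part A has been analysed under SAP 1.0, the Amendment 7 summary describes its C3NeF testing as completed and reported, and the documents identify no subject still to reach Week 48. The cost is SAP and protocol wording plus programming, with no new data, visits or patients. Week 48 spot values that were not collected cannot be recovered.

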#### After investigational product administration:

- Subjects will be contacted via phone by study staff 6 hours after the study treatment to collect safety information (Visit 15 only)
- Vital sign measurements at 30 minutes post dose
  - Visit 15 only: Vital sign measurements to be measured at 30 minutes, 2 hours, and 4 hours post dose
- Injection Site Assessment
- Collect AEs
- Dispense uPCR containers for consecutive collection
  - 3 uPCR containers (Visit 5 and 15 [for subjects entering the follow-up period]), 6
     uPCR containers (Visits 6-10, Visit 14, and, for subjects entering Part B, Visit 15), 9 containers (Visits 11-13)

### 13.3. Part B: Long-Term Extension Phase (Week 48 and Beyond)

At Visit 15 (Day 336; Week 48) subjects will have the opportunity to enter Part B, the Long-Term Extension Phase, at the discretion of the investigator, in order to continue to receive treatment with pegcetacoplan until it is commercially available for the disease under treatment. Subjects who enter the Long-Term Extension Phase will complete study procedures as outlined in Appendix 1 and Table A1.

### **13.4.** Follow-up (Visits 16-20)

All subjects who complete study treatment through Day 336/Week 48 but do not enter the Part B Long-Term Extension Phase will need to return to the clinical site for Follow-up Visits 16, 17, 18, 19, and 20, where the assessments outlined in the schedule of events (Section 4) will be performed.

Subjects who discontinue treatment early and do not continue their participation in the study should complete a follow-up visit 6 weeks after discontinuation of treatment and also the Exit Visit 6 weeks thereafter.

Visit window:  $\pm 2$  days (Visits 16-18)  $\pm 7$  days (Visits 19 and 20)

- Procure 3 previously collected consecutive uPCR samples to site (Visits 16-20)
  - Arrange courier pickup for all biweekly triplicate uPCR samples during non-clinic visit weeks
- Physical examination (Visit 16 and 17 only)
- Concomitant medications review (Visit 16 and 17 only)
- Injection Site Assessment (Visit 16 only)
- Antidrug Ab collection
- eGFR assessment
- Urinalysis collection (See schedule of events for details)
- Urine pregnancy test (Visit 16-19 only)
- AE review
- PK Sample collection
- Vital Signs
- Blood tests (See schedule of events for details)
- Triplicate 12-lead ECG
- Dispense uPCR containers for consecutive collection (Visits 16-20):
  - 3 uPCR containers (Visits 16 and 17), 6 uPCR containers (Visit 20), 9 uPCR containers (Visits 18 and 19)
- Dispense 24-hour urine container

### 13.4.1. Exit Visit (Visit 21)

If subjects are not participating in Part B the Long-Term Extension Phase, they will return to the clinical facility for the Exit Visit 24 weeks after the final dose of pegcetacoplan, on Day 504 (or sooner if the subject discontinues prior to the Week 48).

Study participation for each subject will be concluded following completion of the Exit Visit. If a subject withdraws from the study prior to the scheduled Exit Visit, all Exit Visit evaluations should be performed at the subject's final visit to the clinic, including the collection of blood

samples for PK and/or PD assessments, as well as a postdose antigenicity sample if not yet collected.

The Exit Visit procedures are listed in the Schedule of Events in Section 4.

Visit window:  $\pm 7$  days.

- Arrange courier service to pick up 24-hour urine collection to deliver to site
- Procure 3 previously collected consecutive uPCR samples to site
- Blood tests (see schedule of events for details)
- Concomitant medications
- AE review
- Antidrug Ab assay
- eGFR assessment
- Urinalysis (See schedule of events for details)
- PK Sample
- Vital Signs
- Triplicate 12-lead ECG

### 13.4.2. Unscheduled Follow-up Visits

All subjects will be asked to return to the clinical facility for additional follow-up visits if considered necessary by the PI.

Unscheduled follow-up visits may include (but are not limited to) any of the procedures listed in the Schedule of Events in Section 4.

### 13.4.3. Safety Monitoring Committee

An SMC will review cumulative safety/tolerability data (eg, physical examinations, ECGs, vital signs, clinical laboratory tests, and AEs). The SMC will have the responsibility to conduct a thorough safety assessment at regular predefined intervals during the treatment period of the study.

The first SMC meeting will be scheduled 3 months after the first subject is dosed, and at further 3 monthly intervals until all subjects complete the Week 48 Visit. An *ad hoc* SMC data review may be recommended by the SMC or requested by the sponsor at any time during the study.

The remit, roles, and responsibilities of the SMC will be specified in a separate SMC charter.

### 13.5. Treatment Discontinuation and Study Withdrawal

Subjects will be considered to have completed the study when they have completed the Week 72 exit visit activities described in the Schedule of Assessments in Section 4, when they have enrolled in a subsequent study of pegcetacoplan, or when they have discontinued study treatment and completed any early termination activities.

A subject may withdraw from the study at any time, for any reason, without prejudice to his/her future medical care by the physician or at the institution. If a subject discontinues or is withdrawn from study treatment for any reason, the study site must immediately notify the medical monitor.

Treatment may be discontinued and/or a subject's participation in the study may be discontinued, for any of the following reasons:

- 1. Any serious adverse event (SAE), clinically significant AE, severe laboratory abnormality, intercurrent illness, or other medical condition (including infections) that indicates to the PI that continued participation is not in the best interest of the subject.
- 2. Subject's decision to withdraw.
- 3. Subject's failure to comply with protocol requirements (including pregnancy) or study-related procedures.
- 4. Termination of the study by the sponsor, US Food and Drug Administration, or other regulatory authorities.
- 5. Liver Toxicity (please refer to Section 13.5.1 for further details).
- 6. Sustained and significant reduction in renal function (see more details below).

A sustained and significant reduction in renal function is defined by one of the following: initiation of chronic dialysis, a confirmed and sustained eGFR ≤15 mL/min/1.73 m² or a confirmed and sustained reduction in eGFR of at least 30% which is drug related in the opinion in the PI. A reduction in eGFR would be considered confirmed if present on 2 separate consecutive measurements and sustained if the 2 measurements are at least 1 week or apart.

The reason for treatment discontinuation and/or withdrawal from the study must be recorded in the subject's source document.

Subjects who discontinue study treatment prior to the end of the treatment period, should undergo all follow-up visits and procedures through study completion (Exit Visit), unless unwilling or unable, or consent has been withdrawn. Subjects who wish to fully withdraw from the study before Visit 15, should be encouraged to complete the Early Termination Exit Visit.

Any subject withdrawn due to an AE (whether serious or nonserious) or clinically significant abnormal laboratory test values will be evaluated by the investigator and should be treated and/or followed at least up until the symptoms or values return to normal or acceptable levels, as judged by the PI.

If consent is withdrawn, no further study evaluations are to be performed and no attempts are to be made to collect additional data.

